4.8 Procedures for reporting deviations from the original statistical plan

Under normal circumstances, only the statistical analysis content agreed in advance included in the statistical analysis plan can be presented in the clinical trial report of this trial. The increased demand for statistical analysis for various uncertain reasons is only exploratory analysis.

4.9 Selection criteria and rationale for participants included in the analysis

Full Analysis Set (FAS): All subjects who received at least 1 investigational device treatment and at least one post-baseline observation data will be enrolled in FAS, according to the basic principles of intention-to-treat analysis. FAS will be used as the primary population for baseline data and sensitivity analysis for validity evaluation. Participants may only be excluded in very limited circumstances, including when important inclusion criteria are violated and no observational data are available after enrollment.

Compliant protocol set (PPS): is a subset of FAS, defined as subjects who have measurable lesions at baseline and have completed at least one assessment of primary efficacy indicators after baseline. PPS will be the primary population for the effectiveness evaluation of this study.

Safety dataset (SS): all participants who received at least 1 study device treatment and at least one safety assessment. SS will be the primary population for safety analysis in this study.

The assessment of baseline characteristics will use the full set of analyses; The evaluation of effectiveness will use both the full analysis set and the conforming protocol set; Security analysis uses security datasets.

4.10 Covariate and subgroup analysis

Subgroup analysis as necessary was not precluded. Subgroups include, but are not limited to:

- (1) Tumor sites (tumors of the nervous system, head and neck, chest, abdomen, spine, pelvis, extremities, etc.).

DCR	Disease Control Rate	Tumor disease control rate
ECOG	Eastern Cooperative Oncology Group	Eastern Oncology Collaborative Group
FAS	Full Analysis Set	Full analysis set
ICH	The International Council for Harmonisation of Technical Requirement for Pharmaceuticals for Human Use	International Harmonization Council for Technical Requirements for Pharmaceuticals for Human Use
MedDRA	Medical Dictionary for Regulatory Activities	Medical Dictionary of Regulatory Activities
NYHA	New York Heart Association	New York Heart Society
ORR	Objective Response Rate	Objective response rate
PD	Progressive Disease	Disease progression
PET	Positron Emission Tomography	Positron emission tomography
PN	Preferred Name	Preferred name
PPS	Per-Protocol Set	Conforms to the scenario set
PR	Partial Response	Partial relief
PSA	Prostate Specific Antigen	Prostate-specific antigens
PT	Preferred Terms	Preferred term
SAE	Serious Adverse Events	Serious adverse events
SAP	Statistical Analysis Plan	Statistical analysis plan
SAS	Statistical Analysis System	Statistical analysis system
SD	Stable Disease	Stable disease
SLD	Sum of Longest Diameter	Sum of longest diameters of tumors
SOC	System Organ Class	Systematic organ classification
SS	Safety Set	Security datasets
TEAE	Treatment Emergent Adverse Event	Adverse events during the treatment period
TNM	Tumor, Node, Metastasis	Tumors, lymph nodes, metastases
WHODD	World Health Organization Drug Dictionary	World Health Organization Dictionary of Medicines
WOCF	Worst Observation Carried Forward	Worst observed data carryover

This statistical analysis plan (SAP) refers to the E9 guiding principles of the International Council for Harmonization of Technical Requirements for Pharmaceuticals for Human Use (ICH) Guidance for Industry: Statistical Principles for Clinical Trials ICH E3 Guidance for Industry: Structure and Content of Clinical Study Reports Relevant national regulations and guidelines, according to the clinical study protocol titled "Varian ProBeam360 Proton Therapy System China Clinical Trial (Wuhan)" (version number: V1.0, Version Date: 2024-01-12) developed.

This SAP describes the rules for the presentation and analysis of short-term follow-up efficacy data and safety evaluation data specified in the protocol, and describes in detail the data, variables and statistical methods that need to be summarized and analyzed. Unless otherwise specified, the final analysis of short-term follow-up will be performed in accordance with this plan, and the presentation of statistical analysis results may be fine-tuned to some extent during the statistical analysis phase.

This SAP was established and finalized prior to the locking of this clinical trial database.

1 Overview of the trial

1.1 Objective

1.1.1 Primary purpose

To evaluate whether the main efficacy evaluation index of Probeam360 in radiation therapy for cancer patients reached the target value of the disease control rate (DCR) 3 months after the end of the last treatment. Whether the proportion of CTCAE grade 3 toxicity was lower than the acceptable value, and whether CTCAE grade 4 and 5 toxicity occurred.

1.1.2 Secondary purpose

To evaluate the secondary efficacy of Probeam360 in radiation therapy for cancer patients, objective response rate (ORR), DCR at 1 month and 2 month after the end of last treatment, tumor markers (if required), The reality of the product usability assessment.

To evaluate the proportion of CTCAE grade 1 and 2 toxicity, laboratory tests, ECOG physical condition classification, adverse event rate, serious adverse event rate, and device defect incidence of Probeam360 in radiation therapy for cancer patients.

1.2 Trial design

This trial is a prospective, single-center, single-group target-value trial design.

Prospective: Adopt a research approach that starts now and tracks the future. Prospective studies can clarify the causal relationship, and there are unified standards for diagnosis, detection, and evaluation of the obtained

data, so the data processing is controllable.

Single center: 1 clinical trial institution was selected to carry out the clinical trial.

Single-group target value method: Because the same device for investigational medical devices is radioactive and difficult to obtain, the existing treatment methods are not feasible due to objective conditions, so the single-group target value method is used. Moreover, the applicable population and main evaluation indicators of experimental medical devices can be fully defined and relatively stable, and the main evaluation indicators adopt the effective rate mentioned in the "Guiding Principles for the Technical Review of Clinical Evaluation of Proton Carbon Ion Therapy Systems" (Circular No. 4 of 2018 of the State Food and Drug Administration), which is relatively objective and reproducible. According to the Guidelines for the Technical Review of Clinical Evaluation of Proton Carbon Therapy Systems, the target therapeutic rate of investigational medical devices should be at least 80%, and the expected value is 95%. Among them, the effective definition is: CR+PR+SD (complete response CR, partial response PR, and stable disease SD), which is basically consistent with the definition of tumor disease control rate in this clinical trial. Therefore, no control group was set up in this clinical trial, and a single-group target value method was used to evaluate whether the tumor disease control rate of ProBeam360 reached the target value (80%), whether the proportion of CTCAE grade 3 toxicity, the main safety evaluation index, was lower than the acceptable value (5%), and whether the proportion of CTCAE grade 4 and 5 toxicity was acceptable (0%).

1.3 Statistical assumptions

In this study, a single-group target-value experimental design was adopted, and the hypothesis test was as follows:

$$H0: \pi_1 \leq \pi_0; \quad HI: \pi_1 > \pi_0$$

Test level $\alpha = 0.05$ (two-sided).

Among them, the disease π_1 control rate and its target value of the ProBeam Proton Therapy System for radiation therapy in cancer patients are respectively.

1.4 Number of subjects

This clinical trial intends to enroll 47 subjects. The sample size determination process is as follows:

This clinical study is a clinical validation design of a single group of target values, and the main effectiveness indicator tumor disease control rate is the basis for sample size estimation. According to the "Guidelines for the Technical Review of Clinical Evaluation of Proton Carbon Ion Therapy System" (Announcement No. 4 of 2018 of the State Food and Drug Administration), the target value is set at 80%, the bilateral significance level is 0.05,

the power is 80%, and the sample size estimation professional software PASS 15.0 is used, and the sample size of the experimental group is at least 42 cases calculated by the above parameters. Considering that about 10% of the cases may be dropped out or lost to follow-up during the clinical validation, the sample size of the experimental group was expanded to 47 cases.

In this trial, the two centers adopted competitive enrollment, and the investigators of the two centers were diagnosed, operated and treated according to the requirements of relevant tumor diagnosis and treatment guidelines, norms and consensus, and it is expected that there will be only a few patients in one center, and the center will have little impact on efficacy and safety, and the center effect will no longer be considered in the analysis.

2 Evaluation indicators

2.1 Effectiveness evaluation indicators

2.1.1 Key Effectiveness Indicators

- **Tumor disease control rate (DCR) at 3 months after the end of last treatment**

The occurrence of CR, PR and SD after the end of treatment was considered to be disease control, and the absence of biochemical recurrence at the end of treatment of prostate cancer was considered to be disease control. Proportion of subjects with disease control 3 months after the end of the last radiation therapy.

Calculation formula: $DCR = \text{number of subjects under disease control} / \text{total number of subjects} \times 100\%$

2.1.2 Secondary effectiveness measures

- **Objective response rate (ORR)**

CR or PR was considered objective remission at the end of treatment, no biochemical recurrence occurred at the end of prostate cancer at the end of treatment, and no regional lymph node metastasis or distant metastasis was considered objective remission. Proportion of subjects with objective remission at each time point after the end of the last treatment.

Calculation formula: $ORR = \text{number of subjects with objective remission} / \text{total number of subjects} \times 100\%$

- **Tumor disease control rate (DCR) at 1 month after the end of last treatment**

The occurrence of CR, PR and SD after the end of treatment was considered to be disease control, and the absence of biochemical recurrence at the end of treatment of prostate cancer was considered to be disease control. Proportion of subjects with disease control 1 month after the end of the last treatment.

Calculation formula: $DCR = \text{number of subjects under disease control} / \text{total number of subjects} \times$

100%

- **Tumor markers (if required)**

Tumor marker examination was performed and clinically significant changes in tumor markers (before and after radiation therapy) were reported at the discretion of the investigator.

- **Ease of use (ProBeam System, Radiation Therapy Management Software (Aria), Radiation Therapy Planning Software (Eclipse))**

Investigators using the corresponding functions scored according to the Likert scale and collected open-ended questions to evaluate the comprehensive feeling of ease of use during the treatment.

2.2 Safety evaluation index

2.2.1 Key safety indicators

- **Proportion of CTCAE grade 3 toxicity**

Proportion of subjects with grade 3 toxicity in the trial cycle.

Calculation formula: Proportion of CTCAE grade 3 toxicity = number of subjects with CTCAE grade 3 toxicity in the test cycle / total number of subjects $\times 100\%$;

- **Proportion of CTCAE grade 4 and 5 toxicity**

Proportion of participants with grade 4 and 5 toxicity during the trial cycle.

Calculation formula: Proportion of CTCAE grade 4 and 5 toxicity = number of subjects with CTCAE grade 4 and 5 reactions in the trial cycle / total number of subjects $\times 100\%$;

2.2.2 Secondary safety metrics

- **Proportion of CTCAE grade 1 and grade 2 toxicity**

Proportion of participants with Grade 1 and Grade 2 toxicity in the trial cycle.

Calculation formula: Proportion of CTCAE grade 1 and grade 2 toxicities = number of subjects with CTCAE grade 1 and 2 toxicity in the trial cycle/total number of subjects $\times 100\%$;

- **Laboratory tests (blood routine, coagulation routine, urine routine, liver function, renal function)**

Laboratory tests were performed and, in the judgment of the investigator, clinically significant changes in laboratory markers (before and after radiation therapy was administered) were reported.

- **ECOG Grade of Strength Status**

ECOG performance status grading assessment was performed and clinically significant changes in examination results (before and after radiotherapy) were reported at the discretion of the investigator.

- **Incidence of adverse events**

An adverse event (AE) is an unfavorable medical event that occurs during the course of a clinical trial, whether or not device related.

Calculation formula: incidence of adverse events = number of subjects with adverse events in this group / number of all subjects in this group $\times 100\%$;

- **Incidence of serious adverse events**

A Serious Adverse Event (SAE) is a serious adverse event that occurs during a clinical trial that results in death or serious deterioration of health, including fatal illness or injury, permanent defects in body structure or function, hospitalization or prolonged hospital stay, medical or surgical intervention to avoid permanent defects in body structure or function, fetal distress, Fetal death or congenital anomalies, congenital defects and other events.

Calculation formula: incidence of serious adverse events = number of subjects with serious adverse events in this group / number of all subjects in this group $\times 100\%$;

- **Incidence of device defects**

Device defects refer to the unreasonable risk that medical devices may endanger human health and life safety under normal use during clinical trials, such as crashes.

Calculation formula: incidence of device defects = number of device defects / number of device use $\times 100\%$;

3 Statistical analysis set

The following analysis sets were defined in this trial for statistical analysis.

Full Analysis Set (FAS): According to the basic principles of intention-to-treat analysis, all participants who received at least one treatment with an investigational device and at least one post-baseline observational data will be included in the FAS. FAS will be used as the main population for the baseline data and effectiveness evaluation sensitivity analysis of this study. Exclusion is only possible in very limited circumstances, including cases where important enrollment criteria have been violated and no observational data have been available after enrollment.

Per-Protocol Set (PPS): is a subset of FAS and refers to subjects with measurable lesions at baseline who have completed at least one primary efficacy measure assessment after baseline. PPS will be the main population in the evaluation of the effectiveness of this study.

Safety Set (SS): All participants who received at least one treatment with an investigational device and had at least one safety evaluation. SS will be the primary population for safety analysis in this study.

The baseline characteristics will be assessed using the full analysis set, the effectiveness will be assessed using both the full analysis set and the conformance set, and the safety analysis will use the safety dataset.

4 data processing

4.1 Processing of data from unscheduled visits

The processing of unscheduled event data is agreed as follows:

In addition to the scheduled visit data, unscheduled event data should also be considered when judging the baseline value. Unless otherwise specified, the last non-missing test value before the first treatment is used as the baseline value.

Safety trial (e.g., laboratory tests, vital signs) metrics aggregated by visit, and only scheduled visit test results are summarized.

When performing the worst observational data carry-over and fill (WOCF) analysis for the main effectiveness evaluation indicators, the unplanned event data will be considered in addition to the planned visit data, but only the planned visit data will be descriptively summarized.

All unscheduled event data should be tabulated.

Unless otherwise specified, the data of unscheduled visits will be summarized and tabulated according to the above principles, otherwise they will be described in a footnote under the statistical analysis table.

4.2 Handling of missing dates for various events

For various events (previous/concomitant medications, concomitant treatments, AEs, etc.), according to the definition and nature of different events, the fill-in rules for the absence of their start/end dates are agreed. If the end date of each event is missing, it will not be filled, and the rules for missing the start date are shown in Table 2.

Table 2 Incomplete filling rules with start dates

Missing values	Fill the rules
day	If the year and month are the same as the year and month of the treatment start date, and the end date is after the treatment start date or is missing, the treatment start date is used to fill in; Otherwise fill for 1 day.
Day/Month	If the year is the same as the treatment start date, and the end date is after the treatment start date or is missing, the treatment start date is used to fill in; Otherwise fill for January 1.
Day/Month/Year	If the end date is after the treatment start date or is missing, the treatment start date is used to fill in; Otherwise, no filling will be carried out.

4.3 Effectiveness indicators are missing

When analyzing the main effectiveness evaluation indicators based on PPS, it is not necessary to consider filling them.

In the sensitivity analysis of the main effectiveness evaluation indicators based on FAS, the missing values of the main effectiveness evaluation indicators were not filled.

The missing values of qualitative secondary effectiveness evaluation indicators ORR and DCR were filled by the method of worst observational data carryover (WOCF).

The missing value of the quantitative secondary effectiveness evaluation index DOR was not filled.

Other secondary effectiveness evaluation indicators, such as tumor markers, tumor-specific symptoms, and product ease of use, were not filled.

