4.4 Handling of missing safety indicators

The missing values of safety evaluation indicators were filled by the method of Worst Observational Data Carryover (WOCF).

According to the conservative principle, if the severity of an AE is missing, it will be recorded as "grade 3" in the summary description, and if the relationship between an AE and the investigational medical device is missing, it will be recorded as "probable" in the summary description as "probable".

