5.4 Effectiveness evaluation indicators

5.4.1 Key Effectiveness Indicators

The primary effectiveness evaluation was based on the Full Analysis Set (FAS) and the Protocol-Consistent Set (PPS).

The number and percentage of cases that achieved tumor disease control at 3 months during the follow-up period were calculated, and the 95% confidence interval of tumor disease control rate was calculated by Clopper-

Pearson, and the target value of tumor local control rate was 80%, and if the lower limit of the 95% confidence interval of the test results was greater than 80%, the tumor local control rate was reached. The single-sample chi-square test was used to compare whether there was a statistical difference between the local control rate and the target value.

For the evaluation results of the imaging review team, if the efficacy evaluation results of the two evaluators are consistent, the final evaluation results of the two evaluators will be taken, and if the evaluation results of the two evaluations are inconsistent, the independent evaluation value of the third evaluator will be taken as the final evaluation results.

Based on FAS, the sensitivity analysis of the main effectiveness indicators was carried out, and the missing values of the main effectiveness evaluation indicators were filled by the method of Worst Observational Data Carryover (WOCF).

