5.6 Sensitivity analysis

If the receiver effectiveness index was filled by the worst observational data carry-over (WOCF) method, the sensitivity analysis of the main effectiveness measure was performed based on FAS. When the conclusions of FAS and PPS are consistent, the confidence of the test results can be enhanced. When the conclusions of the two groups are inconsistent, the analysis based on the inclusion of PPS population should be the main one, and the differences should be fully discussed and explained.

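### The SAP gives opposite rules for a missing 3-month DCR in the FAS sensitivity analysis (4.3 does not fill it, 5.4.1 fills it by WOCF), and leaves open the denominator and patients with no tumour reading.

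*SAP*

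**What the plan says.** Several places in the two documents bear on how a missing 3-month DCR is handled in the FAS.

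- **SAP 4.3**, on the sensitivity analysis of the primary indicator: "based on FAS, the missing values of the main effectiveness evaluation indicators were not filled". The next sentence treats the secondary indicators the other way: "The missing values of qualitative secondary effectiveness evaluation indicators ORR and DCR were filled by the method of worst observational data carryover (WOCF".
- **SAP 5.4.1**, also on the FAS sensitivity analysis of the primary indicator: "the missing values of the main effectiveness evaluation indicators were filled by the method of Worst Observational Data Carryover (WOCF".
- **SAP 4.1** tells the programmer which visits to use "When performing the worst observational data carry-over and fill (WOCF) analysis for the main effectiveness evaluation indicators", so it takes for granted that such an analysis exists.
- **SAP 5.6** links the two in a conditional sentence: "filled by the worst observational data carry-over (WOCF) method, the sensitivity analysis of the main effectiveness measure was performed based on FAS". It adds that agreement between FAS and PPS strengthens confidence, and "When the conclusions of the two groups are inconsistent, the analysis based on the inclusion of PPS population should be the main one".
- **SAP 4.4** uses the same method for safety: "The missing values of safety evaluation indicators were filled by the method of Worst Observational Data Carryover (WOCF".
- **Protocol 4.7.2(3)** permits, but does not require, a worst-case estimate for a missing 3-month DCR.
- **Protocol 3.1.4.1 and SAP 2.1.1** define DCR as controlled subjects over all subjects. Neither says how a subject without a 3-month result is counted.
- **SAP 3** admits a treated patient to the FAS on any single post-baseline observation. It need not be a tumour assessment.

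**The concern.** SAP 4.3 and 5.4.1 name the same indicator, the same set and the same sensitivity analysis. They cannot be reconciled by saying that one covers a main FAS analysis and the other a sensitivity analysis. A programmer has to disregard one of them.

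Within 4.3 the effect is odd. Objective response is reported as "Proportion of subjects with objective remission at each time point after the end of the last treatment", which includes 3 months, and its gaps are filled by WOCF. The 3-month DCR comes from the same scans and would not be filled. If unfilled patients are dropped, the two rates would have different FAS denominators.

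At stake is the value of the FAS check. PPS is restricted to FAS patients with a measurable baseline lesion and at least one primary assessment after baseline, and 4.3 does not fill it either. If 4.3 is followed and missing patients are dropped, FAS and PPS analyse nearly the same observed results. Their agreement then shows little.

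WOCF makes the check more informative but leaves two gaps. It has nothing to carry for a FAS patient with no post-baseline tumour reading. It also counts as controlled anyone lost after stable disease or better at every earlier reading.

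**Working it through.** **Inputs from the documents.** Target 80%, expected rate 95%, two-sided 0.05, power 80%, 10% dropout (Protocol summary; Protocol 4.2 to 4.4). Success means a lower 95% limit above 80% (Protocol 4.5), by Clopper-Pearson (Protocol 4.7.1, SAP 5.4.1).

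**The plan's own figure.** n = [1.960 × √(0.80 × 0.20) + 0.842 × √(0.95 × 0.05)]² / 0.15² = 41.6, so 42. Then 42 / 0.90 = 46.7, so 47. Both reproduce.

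**Assumptions, not plan figures.** All 47 are in the FAS, with 1, 3 or 5 missing 3-month results; 5 is 47 − 42. Fewer than 5 is plausible, because the 10% in Protocol 4.4 also covers untreated patients, who are outside the FAS. In the WOCF columns every missing patient has at least one earlier reading.

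**Formula.** For x controlled of n, the lower limit is the 0.025 quantile of Beta(x, n − x + 1).

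| Missing | Observed controlled | Not filled, dropped | WOCF, no carried PD | WOCF, one carried PD | Kept in denominator, or counted as failures |
|---|---|---|---|---|---|
| 1 | 43 of 46 | 82.1% | 82.5% (44/47) | 79.6% (43/47) | 79.6% (43/47) |
| 3 | 41 of 44 | 81.3% | 82.5% (44/47) | 79.6% (43/47) | 74.3% (41/47) |
| 5 | 39 of 42 | 80.5% | 82.5% (44/47) | 79.6% (43/47) | 69.2% (39/47) |
| 5 | 40 of 42 | 83.8% | 85.5% (45/47) | 82.5% (44/47) | 71.7% (40/47) |

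In the last row, WOCF falls below 80% only with a second carried progression (43/47, 79.6%).

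**Which rule is stricter.** I enumerated every combination of observed failures and carried progressions with 1 to 6 missing of 47.

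- If unfilled patients are dropped, every split has the unfilled analysis passing and WOCF failing. Each such split needs at least one missing patient with an earlier PD.
- If unfilled patients stay in the denominator, every split has WOCF passing and the unfilled analysis failing, for example 44/47 (82.5%) against 39/47 (69.2%).

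The direction therefore depends on the denominator, which the documents do not settle.

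**How often a split would occur on the dropped reading.** Assume a true rate of 95% among those observed. If each missing patient has a 5% chance of a carried PD, the probability of a split is about 1%, 3% and 5% with 1, 3 and 5 missing. At a 20% chance it is about 4%, 13% and 22%.

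**The worst-case bound.** The smallest passing count is 44 of 47. With 4 missing, even 43 of 43 observed gives 43/47, or 79.6%. Counting missing as not controlled therefore cannot clear 80% with 4 or more missing.

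**The case against.** The strongest reply is that little depends on this. PPS is the main effectiveness population, is not filled, and prevails if the sets disagree. That stands. A reader might infer that the trial's pass or fail turns on the contradiction, but the documents do not support that. Only the robustness check is affected.

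A reader might also infer that 4.3 is simply the lenient option and WOCF the strict one. That holds only if unfilled patients are dropped; on the other reading of the formula it reverses.

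It is tempting to align Protocol 4.7.2(3) with WOCF, since the SAP applies WOCF to secondary and safety endpoints. But the protocol's worst-case wording can be read as missing equals failure, and rewriting it as WOCF could loosen it.

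Some apparent gaps are mostly closed. The protocol summary and Protocol 3.1.4.1 already count patients who stop before the end of radiotherapy, other than losses to follow-up, as not controlled. The SAP's silence there is not a conflict. Protocol 3.1.4.2 has the review panel assess DCR at earlier visits by RECIST 1.1 and asks for PET-CT confirmation only at 3 months, so an earlier panel PD is naturally a recorded PD that WOCF carries. The patients left unsettled are mainly those lost to follow-up, and those who complete radiotherapy without a tumour assessment.

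Finally, Protocol 4.7.2 leaves missing data to be settled at the blinding review. In an open-label, single-group trial there is no allocation to conceal, so this gives limited protection.

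**Conclusion.** The contradiction between SAP 4.3 and 5.4.1 is real and should be fixed. The sentence in 4.3 is the outlier: 4.1 presupposes WOCF, and 5.6 supports it less firmly because its wording is conditional. The denominator and the class given to FAS patients with no post-baseline tumour assessment are also open.

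The size depends on the assumed counts. With 47 in FAS, 5 missing and 39 observed controlled, the lower limit runs from 69.2% to 82.5% across the readings of the documents. A split can arise with a single missing patient (82.1% against 79.6%), but on the dropped reading it needs an earlier PD among the missing. Neither rule can be called the stricter until the denominator is fixed. The consequence is limited to the FAS check on the PPS result.

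**What to change.** Before database lock:

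1. Correct SAP 4.3 so that the FAS sensitivity analysis of 3-month DCR uses WOCF, in agreement with 5.4.1 and 4.1.
2. State that its denominator is all FAS patients.
3. Count FAS patients with no post-baseline tumour assessment as not controlled.
4. Leave the worst-case wording of Protocol 4.7.2(3) as it is. Honour it with one added row in which every missing result counts as not controlled. Label that row a lower bound and not a pass/fail test, because it fails by construction with 4 or more missing of 47.
5. For clarity, cross-refer in the SAP to the protocol's rule on stopping before the end of radiotherapy.

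Optionally, report how many missing patients would have to be failures to lose the 80% criterion. Four failures among 47 lose it, so the count is 4 minus the observed failures.

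The cost is a few sentences in the SAP and one table row. No new data are needed, and the PPS analysis does not change.
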